10.1.2.4. Unsolicited adverse events

Unsolicited adverse event summaries are including serious adverse events unless specified otherwise.

Missing severity, relationship with study vaccine, and outcome of unsolicited adverse events will not be replaced and will appear as ‘UNKNOWN’ when displayed in a statistical output.

10.1.3. Data derivation

10.1.3.1. Age at first dose in years

When age at first dose is to be displayed in years, it will be calculated as the number of complete calendar years between the date of birth and the date of first dose. For example:

DOB = 10SEP1983, Date of first dose = 09SEP2018 -> Age = 34 years

DOB = 10SEP1983, Date of first dose = 10SEP2018 -> Age = 35 years

10.1.3.2. Temperature

Temperatures will be presented in degrees Celsius (°C). Temperatures reported in degrees Fahrenheit (°F) will be converted as follows:

$$\text{Temperature (Celsius)} = ((\text{Temperature (Fahrenheit)} - 32) \times 5) / 9$$

10.1.3.3. Numerical serology results

Numerical serology results will be derived from the content of IS.ISORRES in the SDTM dataset. For assays with a specific cut-off, the following derivation rules apply:

IS.ISORRES	Derived value
“NEG”, “-“, or “(-)”	cut-off/2
“POS”, “+”, or “(+)”	cut-off
“< value” and value is <= assay cut-off	cut-off/2
“< value” and value is > assay cut-off	value
“> value” and value is < assay cut-off	cut-off/2
“> value” and value is >= assay cut-off	value
“value” and value is < cut-off	cut-off/2
“value” and value is >= cut-off and value is <=ULOQ	value
“value” and value is > ULOQ	ULOQ*
All other cases	missing

*This rule will be used to computed descriptive statistics (GMTs, fold increase, etc). All values might be displayed in scatter plots with individual results.

10.1.3.4. Geometric mean titers (GMTs) and concentrations (GMCs)

Geometric Mean Titre (GMT) or Concentration (GMC) calculations are performed by taking the inverse logarithm of the mean of the log titre or concentration transformations. Non quantifiable antibody titres or concentrations will be converted as described in section 10.1.3.3 for the purpose of GMT/GMC calculation. Cut-off values are defined by the laboratory before the analysis.

10.1.3.5. Onset day

The onset day for an event (e.g. AE, concomitant medication/vaccination) is the number of days between the last study dose and the start date of the event. This is 1 for an event occurring on the same day as a study dose (and reported as starting after study dose).

10.1.3.6. Duration of events

The duration of an event with a start and end date will be the difference between the start and end date plus one day, i.e. an event that starts on 03MAR2018 and ends on 12MAR2018 has a duration of 10 days.

The duration of solicited events will be calculated as the sum of the individual days with the adverse event reported at grade 1 or higher during the solicited event period.

10.1.3.7. Counting rules for combining solicited and unsolicited adverse events

For output combining solicited and unsolicited adverse events, all serious adverse events will be considered systemic events since the administration site flag is not included in the expedited adverse event CRF pages. Unsolicited adverse events with missing administration site flag will also be considered systemic.

Multiple events with the same preferred term which start on the same day are counted as only one occurrence.

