8.3.3. Regulatory reporting requirements for SAEs and other events

Once an investigator (or designee) becomes aware that a study participant has experienced an SAE/pIMD, he/she must report it to GSK using the required documentation, and within the timeframes, mentioned in the [Table 11](#). This is essential for meeting legal obligations and ethical responsibilities for participant safety and the safety of a study intervention under clinical investigation.

For SAEs/pIMDs, the investigator will always provide an assessment of causality at the time of the initial report, as defined in the Section [10.3.8.2](#).

Local regulatory requirements and sponsor policy for the preparation of an investigator safety report for Suspected Unexpected Serious Adverse Reactions (SUSAR) must be followed. These reports will be forwarded to investigators as necessary.

The sponsor has a legal responsibility to notify local authorities and other regulatory agencies about the safety of a study intervention under clinical investigation. The sponsor will comply with country-specific regulatory requirements related to safety reporting to the regulatory authority, IRB/IEC, and investigators.

Please refer to Section [10.3.9](#) for further details regarding the reporting of SAEs/pIMDs.

CONFIDENTIAL213569 (RSV OA=ADJ-011 EXT:002 MTH20)
Protocol Amendment 1 Final**Table 11 Timeframes for submitting serious adverse events and other events reports to GSK (Amended 4 November 2020)**

Type of Event	Initial Reports		Follow-up of Relevant Information on a Previous Report	
	Timeframe	Documents	Timeframe	Documents
SAEs	24 hours* ††	electronic Adverse Events Form and corresponding Expedited Adverse Event Form	24 hours*	electronic Adverse Events Form and corresponding Expedited Adverse Event Form
pIMDs	24 hours** ††	electronic Adverse Events Form and corresponding Expedited Adverse Event Form	24 hours*	electronic Adverse Events Form and corresponding Expedited Adverse Event Form

* Timeframe allowed after receipt or awareness of the information by the investigator/site staff.

**Timeframe allowed once the investigator determines that the event meets the protocol definition of a pIMD.

†† The investigator will be required to review the SAE/pIMD causality within 72 hours of submission of the SAE/pIMD.
Date/time of the causality review should be entered in the eCRF.**8.3.3.1. Contact information for reporting of SAEs and pIMDs****Table 12 Contact information for reporting of SAEs and pIMDs**

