10.3.8.3. Assessment of outcomes

The investigator will assess the outcome of all unsolicited AEs (including SAEs) recorded during the study as:

- Recovered/resolved.
- Recovering/resolving.
- Not recovered/not resolved.
- Recovered with sequelae/resolved with sequelae.
- Fatal (SAEs only).

10.3.9. Reporting of SAEs, pIMDs**10.3.9.1. Events requiring expedited reporting to GSK (Amended 4 November 2020)**

Once an investigator becomes aware that an SAE/pIMD has occurred in a study participant, the investigator (or designee) must *report the SAE/pIMD* WITHIN 24 HOURS *by completing an Adverse Events Form and a corresponding Expedited Adverse Event Form*. These *forms* will always be completed as thoroughly as possible with all available details of the event.

Even if the investigator does not have all information regarding an SAE/pIMD, the *forms* should still be completed within 24 hours. Once additional relevant information is received, the report should be updated WITHIN 24 HOURS. The investigator will always provide an assessment of causality at the time of the initial report.

Refer to the [Table 11](#) for the details on timeframes for reporting of SAEs/pIMDs.

The investigator will be required to review the SAE/pIMD causality within 72 hours of submission of the SAE/pIMD. *Date/time of the causality review should be entered in the eCRF.*

Refer to the Section [10.3.9.2](#) for the back-up system in case the electronic reporting system does not work.

CONFIDENTIAL213569 (RSV OA=ADJ-011 EXT:002 MTH20)
Protocol Amendment 1 Final**10.3.9.2. Back-up system in case facsimile or electronic reporting system does not work (Amended 4 November 2020)**

In rare circumstances if the electronic reporting system does not work, the investigator (or designee) must fax completed, dated and signed paper Expedited Adverse Event Report to the Study Contact for Reporting SAEs/pIMDs (refer to the [Sponsor Information](#)) or to GSK Clinical Safety and Pharmacovigilance department within 24 hours.

Investigator (or designee) must complete the electronic *Adverse Events Form and the corresponding* Expedited Adverse Event *Form* within 24 hours upon electronic reporting system is resumed. The information reported through the electronic SAE reporting system will be considered valid for regulatory reporting purposes.

CONFIDENTIAL213569 (RSV OA=ADJ-011 EXT:002 MTH20)

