5.2. Primary endpoint(s)

5.2.1. Analysis planned in the protocol

5.2.1.1. Safety analysis

The safety analysis will be performed on the ES for all participants.

A descriptive analysis by group and overall will present a summary of:

- The number and percentage of participants with at least one administration site event (solicited and unsolicited), with at least one systemic event (solicited and unsolicited) and with any AE during the 4-day or 30-day follow-up period will be tabulated with exact 95% CI after Dose 3. The same computations will be done for Grade 3 AEs, Grade 3 non-serious AEs, related AEs and AEs resulting in a medically attended visit.
- The number and percentage of participants reporting each individual solicited administration site event (any grade, Grade 3, with medically attended visit) and solicited systemic event (any grade, Grade 3, with medically attended visit) during the 4-day follow-up period (i.e., on the day of vaccination and 3 subsequent days) will be tabulated for each group after Dose 3.
- For fever, the number and percentage of participants reporting fever by half degree ($^{\circ}\text{C}$) cumulative increments during the 4-day follow-up period (i.e., on the day of vaccination and 3 subsequent days) will be tabulated for each group after Dose 3.
- The number and percentage of participants with any unsolicited AEs during the 30-day follow-up period (i.e., on the day of vaccination and 29 subsequent days) with its exact 95% CI will be tabulated by group and by Medical Dictionary for Regulatory Activities (MedDRA) preferred term. The same tabulation will be done for Grade 3 unsolicited AEs, for any causally related unsolicited AEs, for Grade 3 causally related unsolicited AEs and for unsolicited AEs resulting in a medically attended visit. The verbatim reports of unsolicited AEs will be reviewed by a qualified person and the signs and symptoms will be coded according to the MedDRA Dictionary for Adverse Reaction Terminology. Every verbatim term will be matched with the appropriate Preferred Term.
- The number and percentage of participants with at least one report of SAE/pIMD classified by the MedDRA Preferred Terms and reported during the 30-day follow-up period (i.e., on the day of vaccination and 29 subsequent days) will be tabulated with exact 95% CI. The same tabulation will be done for related SAEs/pIMDs. SAEs/pIMDs will also be described in detail.

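### SAP 10.1.3.7 counts every SAE as systemic in combined tables, so a serious injection-site reaction can be missing from the administration-site rows of the first primary safety table

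*SAP*

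**What the plan says.** SAP 10.1.3.7 sets two defaults for output that combines solicited and unsolicited events. For SAEs, "all serious adverse events will be considered systemic events since the administration site flag is not included in the expedited adverse event CRF pages". For the rest, "Unsolicited adverse events with missing administration site flag will also be considered systemic". Both SAP versions carry the same text.

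The first bullet of SAP 5.2.1.1 is a table of this kind. With exact 95% CIs, over the 4-day or 30-day period, it counts participants "with at least one administration site event (solicited and unsolicited), with at least one systemic event (solicited and unsolicited") and participants with any AE. It then adds: "The same computations will be done for Grade 3 AEs, Grade 3 non-serious AEs, related AEs and AEs resulting in a medically attended visit". SAP 10.1.2.4 brings SAEs into the unsolicited component: "Unsolicited adverse event summaries are including serious adverse events unless specified otherwise".

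On data collection, Protocol Table 11 has SAEs submitted on the "electronic Adverse Events Form and corresponding Expedited Adverse Event Form". Protocol 10.3.9.1 repeats this: the SAE is reported "by completing an Adverse Events Form and a corresponding Expedited Adverse Event Form". The documents do not include the CRF, and no section says which of the two forms holds the administration-site flag for an SAE.

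**The concern.** The table separates local from systemic reactogenicity under a primary objective of an uncontrolled study. For SAEs, the rule makes that separation by form type and ignores where the event occurred. An injection-site infection that leads to hospital admission would be counted as systemic even if its coded term named the injection site. The error can run only one way: serious site events leave the administration-site rows and enter the systemic rows.

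The reason given is that one set of pages lacks a flag. The protocol asks for a second form for the same event, and the SAP's own sentence on missing flags shows that a site flag is collected for unsolicited AEs. The rule does not say why neither that form nor the coded term is used. In a sparse row, such as Grade 3 administration-site events, the table could show zero although a serious Grade 3 site reaction had occurred.

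**Working it through.** The plan states no figure on this point, so there is nothing to reproduce. The check is a reading of the rules against each other, followed by an illustration of size.

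**1. Does the rule reach the primary table?** Yes. SAP 10.1.3.7 governs combined output, the first bullet of SAP 5.2.1.1 combines solicited and unsolicited events, and SAP 10.1.2.4 includes SAEs.

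**2. Who actually moves?** The table counts participants with at least one event, so a participant leaves an administration-site row only if the SAE was the sole site event qualifying for that row.

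- *Any row:* a counted diary event (pain, erythema or swelling) or a flagged non-serious site AE keeps the participant in.
- *Grade 3 row:* the other site event must itself be Grade 3.
- *Related row:* any counted solicited site event is enough, because Protocol 10.3.8.2 treats all solicited events as related.
- *Medically attended row:* the other site event must be medically attended.

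The systemic row rises only if the participant has no other qualifying systemic event.

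**3. What does the SAE clause leave unchanged?** The any-AE row (the event still counts), the Grade 3 non-serious rows (SAEs are excluded) and the SAE tables by preferred term (SAP 5.2.1.1 and 5.3.1.3).

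**4. Size.** Inputs:

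- n ≈ 100 per group (Protocol Table 4), and 3 × 100 ≈ 300 overall.
- Clopper-Pearson intervals (SAP 10.1.5.1).
- Number of serious site reactions: not given in the documents; assumed 0 to 2 in about 300.

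The shift per participant moved is 100/n points: 100/100 = 1.0 and 100/300 = 0.3.

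The 95% limits for x of n are the 0.025 quantile of Beta(x, n − x + 1) and the 0.975 quantile of Beta(x + 1, n − x). For x = 0 the lower limit is 0 and the upper limit is 1 − 0.025^(1/n), which gives 3.62% at n = 100 and 1.22% at n = 300.

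| Administration-site row (assumed counts) | Counted by site | Shown under the rule |
|---|---|---|
| Sparse, n = 100 | 1/100 = 1.0% (0.03–5.45) | 0/100 = 0% (0–3.62) |
| Sparse, n = 100 | 3/100 = 3.0% (0.6–8.5) | 2/100 = 2.0% (0.2–7.0) |
| Common, n = 100 | 71/100 = 71.0% (61.1–79.6) | 70/100 = 70.0% (60.0–78.8) |
| Sparse, n = 300, one moved | 1/300 = 0.3% (0.01–1.84) | 0/300 = 0% (0–1.22) |
| Sparse, n = 300, two moved | 2/300 = 0.7% (0.1–2.4) | 0/300 = 0% (0–1.22) |

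**5. Allowing for other site events.** If a share q of such participants have another qualifying site event, the expected shift per serious site reaction is (1 − q) × 100/n.

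| q | n = 100 | n = 300 |
|---|---|---|
| 0 | 1.0 point | 0.33 point |
| 0.5 | 0.5 point | 0.17 point |
| 0.9 | 0.1 point | 0.03 point |

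**The case against.** The strongest defence is that the rule is prespecified and disclosed, rests on a factual statement about the CRF, and hides nothing. SAEs within 30 days and over the whole study are tabulated by preferred term with exact CIs and described in detail, so a serious injection-site event would be seen. That stands, and it limits the point to classification within one table.

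A reader might infer three stronger things that the documents do not support.

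- *That Protocol Amendment 1 made the SAP's reason obsolete.* The protocol does not contradict the statement that the expedited pages lack the flag. Both SAP versions (1 December 2020 and 15 July 2021) post-date and cite Amendment 1 (4 November 2020). That the Adverse Events Form carries the flag for SAEs is only a possibility. What can be said is that the reason does not address the second form.
- *That the rule removes the most severe local reactions.* Protocol 10.3.8.1 separates seriousness from Grade 3. Severe but non-serious site reactions, such as pain preventing normal activity or swelling above 100 mm, stay in the site rows.
- *That every serious site reaction drops out, or that a count of serious local events is altered.* The condition in step 2 of the working applies, and no row for serious administration-site events is planned.

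It can also be said that coded terms are an imperfect guide to site. SAP 5.2.2.1.3 itself maps solicited injection-site erythema to the plain term *Erythema*. This is true, but an event with a non-specific term would simply keep the systemic default, so a term-based step does no worse than the present rule.

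**Conclusion.** The point holds as a minor one. As written, the rule puts a serious injection-site reaction in the systemic category of the first primary safety table, and the participant is lost from an administration-site row when no other site event qualifies for that row. The justification is incomplete, because it does not deal with the Adverse Events Form or the coded term. It has not been shown to be false.

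The maximum effect is 1.0 point per participant moved at n = 100 and 0.3 point at n = 300. It is visible mainly in sparse rows such as Grade 3. The realised effect is probably zero or near zero. This rests on the assumed 0 to 2 serious site reactions in about 300 and on the nominal group size; with fewer enrolled, the shift is 100/n. Nothing here changes the any-AE row, the SAE tables by preferred term or the immunogenicity analyses.

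**What to change.** Check whether the Adverse Events Form completed for an SAE carries the administration-site flag. Then replace the first sentence of SAP 10.1.3.7 with an ordered rule:

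1. If a site flag is available for the SAE, classify by the flag.
2. If no flag is available, classify the SAE as administration-site when its MedDRA term is an injection-, administration- or vaccination-site term.
3. Otherwise keep the systemic default.

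Apply steps 2 and 3 to unsolicited AEs with a missing flag as well; for those events the Grade 3 non-serious rows could also change. Footnote the number of events classified by term. If the sponsor prefers to keep its standard rule, a footnote stating it in the table is the minimum.

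The cost is a short SAP edit and a little programming. No new data are needed, because the events are already coded to MedDRA. The drawbacks are a small departure from the sponsor's standard business rule and the remaining default to systemic for non-specific terms such as *Erythema*.

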10.1.3.8. Counting rules for occurrences of solicited events

When the occurrences of solicited events are summarized, each event recorded as having occurred during a specific period will be counted as only one occurrence regardless of the number of days on which it occurs. Also, in the case of co-administered study interventions, an administration site event recorded for a participant following multiple study interventions will be counted as only one occurrence.

10.1.4. Display of decimals

10.1.4.1. Percentages

Percentages and their corresponding confidence limits will be displayed with one decimal except for 100% in which case no decimal will be displayed.

10.1.4.2. Demographic/baseline characteristics statistics

The mean, median, and standard deviation for continuous baseline characteristics will be presented with one decimal.

The minimum and maximum values and quartile values (if required) will be presented with the same number of decimals as the observed values

The maximum and minimum of transformed body temperatures will be displayed with one decimal.

10.1.4.3. Serological summary statistics

For each assay, geometric mean titers (GMT) or concentrations (GMC) and their confidence limits will be presented with one decimal, as well as GMT/GMC fold increase from pre-dose.

The mean, median, standard deviation and quartile values for frequency of RSVPreF3 specific-CD4+ and CD8+ T cells and for the fold increase (post over pre-vaccination) will be presented with one decimal. The minimum and maximum values will be presented with no decimal.

10.1.5. Statistical methodology

10.1.5.1. Exact confidence intervals around proportions

The exact confidence intervals around within-group proportions are derived using the method of Clopper and Pearson [[Clopper](#), 1934].

PD	Protocol Deviation
PPS	Per-Protocol Set
SAE	Serious adverse event
SAP	Statistical Analysis Plan
SBIR	GSK Biologicals Internet Randomisation System
SD	Standard Deviation
SDTM	Study Data Tabulation Model
UL	Upper Limit of the confidence interval

CONFIDENTIAL

213569 (RSV OA=ADJ-011 EXT:002 MTH20)

Statistical Analysis Plan

1. DOCUMENT HISTORY

Date	Description	Protocol Version
1 DEC 2020	First Version	Amendment 1: 4 NOV 2020

CONFIDENTIAL

213569 (RSV OA=ADJ-011 EXT:002 MTH20)

Statistical Analysis Plan

2. OBJECTIVES/ENDPOINTS

Objectives	Endpoints
Primary	

 To evaluate the safety and reactogenicity following intramuscular (IM) administration of RSVPreF3 OA investigational vaccine up to 1 month post-Dose 3, for all participants. 	
 Occurrence of solicited adverse events (AEs) up to 4 days post-Dose 3 (Day 4). Occurrence of unsolicited AEs up to 30 days post-Dose 3 (Day 31). Occurrence of serious adverse events (SAEs)/ Potential immune mediated diseases (pIMDs) up to 30 days post-Dose 3 (Day 31).

 To evaluate the humoral immune response following IM administration of RSVPreF3 OA investigational vaccine up to 1 month post-Dose 3, for participants vaccinated with 2 doses of RSVPreF3 OA investigational vaccine in the parent study. 	
 Humoral immune response at 1 month post-Dose 3 (Day 31) in terms of: 
 Neutralizing antibody titers against Respiratory Syncytial Virus (RSV)-A Neutralizing antibody titers against RSV-B
Secondary	

 To evaluate the humoral and cell-mediated immune (CMI) response following IM administration of RSVPreF3 OA investigational vaccine up to 1 month post-Dose 3, for participants vaccinated with 2 doses of RSVPreF3 OA investigational vaccine in the parent study. 	
 Humoral immune response at 1 month post-Dose 3 (Day 31) in terms of: 
 RSVPreF3-specific Immunoglobulin G (IgG) antibody concentrations CMI response at 1 month post-Dose 3: 
 Frequency of RSVPreF3-specific CD4+ T-cells identified as expressing at least 2 markers among IL-2, CD40L, TNF-α, IFN-γ

 To evaluate the safety and reactogenicity following IM administration of RSVPreF3 OA investigational vaccine up to the study end, for all participants. 	
 Occurrence of SAEs from vaccination (Day 1) up to study end (Month 6). Occurrence of pIMDs from vaccination (Day 1) up to study end (Month 6).
Tertiary	

 To further characterize immune responses following IM administration of RSVPreF3 OA investigational vaccine up to 1 month post-Dose 3, for participants vaccinated with 2 doses of RSVPreF3 OA investigational vaccine in the parent study. 	
 Any further exploratory immunology such as, but not limited to: 
 Antibodies against specific protein F epitopes. Potential new immunological markers for protection. Frequency of RSVPreF3-specific CD4+ and/or CD8+ T cells expressing one or any combination of immune marker(s) in vitro.

[figure not shown]
CONFIDENTIAL

213569 (RSV OA=ADJ-011 EXT:002 MTH20)
Statistical Analysis Plan

